4.3 Exclusion criteria

A potential subject who meets any of the following criteria will be excluded from participation in this study:

- Patients that are incompetent to make a decision themselves.
- Age <18
- Unstable medical situation due to a disorder not being NA or a leg amputation.

4.4 Sample size calculation

This project primarily aims to provide an insight and preliminary evaluation of utilizing NFC-equipped stickers to increase self-efficacy in home exercise programmes. As this is an exploratory pilot study, no formal power analysis has been conducted. We aim to include 30 patients spread across control and intervention group. This includes patients with a lower extremity amputation and Neuralgic Amyotrophic patients. If the pilot is successful, the data provided can be used to expand the research and calculate a sample size for randomized controlled trials.

5. TREATMENT OF SUBJECTS

5.1 Investigational product/treatment

This pilot aims to provide insight in the feasibility of “smart” (NFC-equipped) stickers accompanied by an app in increasing self-efficacy to physical therapy exercises at home.

In the present course of therapy, supporting their home exercise program, patients suffering from Neuralgic Amyotrophy or a lower extremity amputation (using a socket or an osseointegrated prosthesis) receive a folder with written instructions on performing the exercises which can be consulted when needed. Patients give feedback during every regular hospital visit regarding their exercises and progression. In these sessions, the physiotherapist asks for information on the whole week schedule, whereas for patients it is hard to remember the exercises of the beginning of the week. To improve this, the osseointegrated prostheses patients keep a daily paper-based diary for pain scale, pain location, prosthesis wearing time and time spent on muscle exercises and standing or walking. Apart from this, patients do not register or monitor their progress in current course of therapy.

The introduction of the sticky reminders in combination with the app alters the method of registration compared to the present course, but the overall process remains the same. Instead of written or spoken instructions and feedback, this information will be digitally provided and available. The details of these stickers and app are found in “Paragraph 6.1: Name and description of investigational product(s)”.

5.2 Use of co-intervention (if applicable)

Not applicable

5.3 Escape medication (if applicable)

Not applicable

6. INVESTIGATIONAL PRODUCT

6.1 Name and description of investigational product(s)

To address the self-efficacy and to empower patients in performing exercises, Radboud REshape is developing an innovative intervention in close collaboration with a company called Touchless Industries. Together, they came up with a sticker, equipped with the recently developed NFC technology. NFC is a technology that has emerged and is still growing in availability. Estimates by Statista (one of the world's leading statistics portals gathering data from more than 18.000 sources) show a expected number of 1.9 billion NFC-enabled smartphones in 2018 (Statista, 2013). However, this includes Apple iPhones, whose NFC technology is not freely accessible by all apps. IHS Markit (claiming to be the leading source of information, insight and analytics in critical areas that shape today's technology ecosystem) has estimated that by 2018, 844 million, or 75 percent of Android phones will be equipped with accessible NFC technology (IHS, 2014). Furthermore, mobile network providers (such as the Dutch provider KPN) have started to equip their SIM cards with NFC technology, which supersedes the need for NFC technology on the mobile device itself (KPN, n.d.). Thus, although the market is still growing, a wide availability for NFC smartphones shall be present in the near future.

The developed NFC-stickers are called sticky reminders (see above) and should be placed at locations where certain exercises can be performed. Bringing a NFC-compatible smartphone in close proximity to the sticker automatically launches a video or app on the smartphone, in this case showing an instruction for your exercise. The mobile device application is called "Touchless Fysio", which distinguishes between physiotherapist and patient. Using these stickers, the patient is visually reminded and receives exercise instructions at a location where he/she can perform the exercise immediately. The Sticky Reminders in combination with Touchless Fysio is the investigational product. Since this intervention does not give medical advice, it is not regarded as a medical device and thus does not have a Conformité Européenne (CE) mark. The videos are static and are recorded when the subject visits the physiotherapist and are not altered based on registrations in the mobile application. The physiotherapist does not change the treatment approach in between visits. The information that is registered in the application is in current care registered in a journal or provided orally during a visit. Next to that, the application is not an alternative treatment, but it complements regular care.

For NA patients, videos of the individual him/herself will be linked to the stickers, as they are often filmed during (usually biweekly) physiotherapy sessions already. The video's however will not contain personal features like the face of the patient. Only the back of the patient is filmed. These videos can be uploaded using an online portal. Prosthesis wearers, however, will see generic instruction videos due to frequent physiotherapy sessions (2 times a week), time limitations and a wide variety of possible exercises within their rehabilitation.

The stickers will be supported by the patient application which records all activities on the sticky reminder and securely stores this information. All data will be coded and encrypted and stored on an ISO 27001 certified platform. This application will provide the back-end for the content on the stickers and link the videos to the users. This platform also allows feedback between physiotherapist and patient through logins and daily reports. The application is split into two user interfaces, one for the physiotherapist (web-based) and one for the patient (app-based):

Patient: Sees how many exercises are provided to him/her and how much he/she still needs to accomplish on a daily basis. The patient can also provide feedback to the physiotherapist and to themselves via daily reports or log-ins. In addition, the app will show a timeline with desirable targets, which should provide an extra motivation to perform the exercises.

Physiotherapist: Physiotherapists can easily connect the appropriate video and sticker combination at the desired moment in the rehabilitation via a web-interface. The physiotherapist can log in to this interface and see all the appropriate anonymized patients (per disorder). For each patient, the physiotherapist can look into collected data on log-ins and daily reports, and adapt the therapy accordingly if necessary.

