3. STUDY DESIGN

This pilot is a controlled mixed methods feasibility trial.

The Radboudumc department REshape & Innovation Center in collaboration with two physiotherapy departments will execute the pilot. The envisioned duration of the project is five months. Patients will be included in April and May 2018, after which we will analyse data and publish results. The product-testing period is 4 weeks per patient. There will be an intervention group and a control group. The control group will only execute point 1 and 5 in the research design described below besides their regular treatment (excluding interview and SUS component). The control group is present to exclude conclusions based on treatment effects instead of intervention effects. The intervention group will go through all five steps. Millen et al. chose a similar study design, where they measured self-efficacy in cardiac rehabilitation (Millen *et al.*, 2009).

In the present course of therapy, supporting their home exercise program, patients suffering from Neuralgic Amyotrophy or a lower extremity amputation (using a socket or an osseointegrated prosthesis) receive a folder with written instructions on performing the exercises which can be consulted when needed. Patients give feedback during every hospital visit regarding their exercises and progression. In these sessions, the physiotherapist asks for information on the whole week schedule, whereas for patients it is hard to remember the exercises of the beginning of the week. To improve this, the osseointegrated prostheses patients keep a daily paper-based diary for pain scale, pain location, prosthesis wearing time and time spent on muscle exercises and standing or walking. Apart from this, patients do not register or monitor their progress in current course of therapy.

The introduction of the sticky reminders in combination with the app alters the method of registration compared to the present course, but the overall process remains the same. *Instead of written or spoken instructions and feedback, this information will be digitally provided and available.*

The patient process is described and depicted below.

1. **Baseline measurement:** To monitor self-efficacy patients are asked to fill out a validated self-efficacy questionnaire. This outcome is supposed to be the baseline value of the pilot. For extra information regarding the patient, demographic questions will be included in the questionnaire.

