4.2 Inclusion criteria

In order to be eligible to participate in this study, a subject must meet all of the following criteria:

Intervention group:

- Willing to participate and to provide informed consent
- Minimal remaining rehabilitation period of 4 weeks
- Access to NFC-compatible smartphone
- Within their rehabilitation program, included patients have exercises to perform at home.
- Patient is able to speak, read and understand Dutch

Control group:

- Willing to participate and to provide informed consent
- Minimal remaining rehabilitation period of 4 weeks
- Within their rehabilitation program, included patients have exercises to perform at home.
- Patient is able to speak, read and understand Dutch

These inclusion criteria show that patients who are excluded from the intervention group can be included in the control group. Therefore, patients will be asked whether they have a NFC-compatible smartphone at the start of inclusion. At this point, most Android smartphones are NFC-compatible. This makes the study not truly randomized, but seems reasonable as this is a pilot study.

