8.2 Randomisation, blinding and treatment allocation

We will randomise the allocation of patients to study groups as much as possible within the patient (and NFC) availability pool. Blinding is not appropriate for this pilot.

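### Diagnosis determines the version of the app and the background care, yet neither allocation nor analysis uses it, so an uneven diagnosis mix can distort the comparison of ESES between arms

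*Protocol*

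**What the plan says.** **Intervention.** Under section 6.1, for NA patients "videos of the individual him/herself will be linked to the stickers", because they are "often filmed during (usually biweekly) physiotherapy sessions already". Prosthesis wearers "will see generic instruction videos due to frequent physiotherapy sessions (2 times a week"), with time limits and the variety of exercises as further reasons. Section 12.1 confirms that prosthesis wearers watch an unknown person, and adds that physiotherapists already use those videos in regular care.

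**Usual care.** Section 3 says that "the osseointegrated prostheses patients keep a daily paper-based diary". It describes no such self-monitoring for the other patients.

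**Numbers.** Section 4.4 aims for 30 patients over both arms. "This includes patients with a lower extremity amputation and Neuralgic Amyotrophic patients", but no number is fixed per arm or per diagnosis.

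**Allocation.** Section 8.2: "We will randomise the allocation of patients to study groups as much as possible within the patient (and NFC) availability pool". Under section 4.2, patients without an NFC phone can enter only the control group: "This makes the study not truly randomized, but seems reasonable as this is a pilot study".

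**Analysis.** Section 10.1 names paired t-tests or Wilcoxon signed rank tests, both within and between groups, with no diagnosis term. Section 10.3 lists seven demographic factors for exploratory testing. Diagnosis is not one of them.

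**The concern.** The control group is there so that the ordinary course of rehabilitation is not mistaken for an effect of the app (section 3). It does that job only if the arms have a similar mix of background care, and that care depends on diagnosis.

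The protocol's own rationale makes diagnosis relevant to the endpoint. Section 1 says that personalised programmes raise self-efficacy and counts videos of the patient among the ways in which the reminders personalise. Only NA patients get such videos. The gain over usual care may be smaller for prosthesis wearers, whose generic videos are already in use, and for osseointegrated patients, who already keep a diary.

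At stake is the reading of one small trial. Effect on self-efficacy is a listed feasibility element (section 8.1.2), and the data may be used to size later randomised trials (section 4.4). A contrast that depends on an uncontrolled mix of two versions of the intervention is a poor input for that.

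**Working it through.** The protocol states no effect size, SD or power, so there is no figure of its own to reproduce.

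**Inputs**
- From the protocol: N = 30 (section 4.4); significance at 0.05 (section 10), taken as two-sided.
- Assumed: 15 patients per arm and 15 NA patients as base case, varied from 10 to 20 for each; simple random allocation; a difference δ between diagnoses in 4-week ESES change of 0.25, 0.5 or 1.0 SD, where SD is that of the change within a diagnosis.

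**1. How often is the mix uneven?** In the base case, P(k NA patients in the intervention arm) = C(15,k) × C(15,15−k) / C(30,15), with C(30,15) = 155,117,520. Each split counts in both directions.

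| NA split | Calculation | Probability |
|---|---|---|
| 8 v 7 (best possible) | 2 × 6435² / 155,117,520 | 53% |
| 9 v 6 or worse | 1 − 0.534 | 47% |
| 10 v 5 or worse | 0.466 − 2 × 5005² / 155,117,520 = 0.466 − 0.323 | 14% |
| 11 v 4 or worse | 0.143 − 2 × 3003² / 155,117,520 = 0.143 − 0.116 | 2.7% |

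Over the assumed range of splits, a gap of at least 20 percentage points between arms has probability 25 to 47%, and a gap of at least 33 points 5 to 14%.

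**2. How far does the contrast move?** Shift = δ × (NA share in one arm − NA share in the other). At 10 v 5 the gap is 10/15 − 5/15 = 1/3:
- δ = 0.25: 0.08 SD
- δ = 0.5: 0.17 SD
- δ = 1.0: 0.33 SD

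At 9 v 6 the gap is 0.20, and δ = 0.5 to 1.0 gives 0.10 to 0.20 SD. The standard error of an arm difference with 15 per arm is √(2/15) = 0.365, or about 0.37 SD.

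**3. What does adjustment do?** A simulation with no true app effect compared a two-sample t-test of change with a linear model on arm and diagnosis.

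| Allocations | δ | False positives, unadjusted | False positives, adjusted |
|---|---|---|---|
| All | 0 | 5.0% | 4.8% |
| All | 0.5 | 5.0% | 5.0% |
| All | 1.0 | 5.3% | 5.2% |
| 10 v 5 or worse, more NA on the app | 0.5 | 7.3% | 5.2% |
| 10 v 5 or worse, more NA on the app | 1.0 | 11.9% | 4.4% |

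In the last two rows the mean unadjusted shift was 0.19 and 0.37 SD; adjusted, it was about zero. Over all allocations, adjustment changed the standard error from 0.36 to 0.37 SD when diagnosis had no effect, and from 0.41 to 0.37 SD when δ was 1.0.

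**4. The part that is not chance.** Phone access sends some patients to control only. The protocol gives no phone access by diagnosis, so the resulting imbalance cannot be sized. The probabilities in step 1 do not cover it.

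**The case against.** A reader might infer that a chance mix of diagnoses is likely and can drive the result. The documents do not support that. The best possible split in the base case is also the most common one (53%), and 10 v 5 or worse occurs in at most 14% of allocations over the splits considered. At 10 v 5 the shift stays below one standard error even at δ = 1.0. Chance imbalance is already allowed for in the test's average error rate; the 7 to 12% figures arise only after selecting unfavourable draws in one direction.

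Nor can diagnosis be called a strong prognostic factor. No section gives an ESES difference by diagnosis, and a stable difference in level largely cancels in a before-after change. Only a difference in 4-week change matters, and that could be near zero. An imbalance would not be indistinguishable from an app effect either: diagnosis is known for every patient (the code names in section 12.1 depend on it), so the imbalance would be visible.

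It can also be said that this is an exploratory pilot, that the two types of video are deliberate and justified, and that covariates may be left to an analysis plan. The first two points stand and limit the weight of the concern. The third stands only in part: allocation belongs in section 8.2, and section 10.1 itself fixes the primary tests.

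Finally, the word used for the NA visit schedule is ambiguous, but section 6.1 sets it against the frequent sessions of prosthesis wearers, so the schedules are evidently meant to differ.

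**Conclusion.** The concern holds in a moderate form: an uneven diagnosis mix can distort the arm comparison of ESES, and the protocol neither prevents this nor adjusts for it. In the base case, about one random allocation in seven would be 10 v 5 or worse. The shift at 10 v 5 would be about 0.08 to 0.33 SD for an assumed diagnosis difference of 0.25 to 1.0 SD in ESES change, against a standard error of about 0.37 SD. The 15/15 splits and the diagnosis difference are assumptions. Under true randomisation the harm is to the single realised trial, not to the average type I error; allocation by phone access could add a systematic part of unknown size. Even with balanced arms, the before-after result in the intervention arm averages two versions of the intervention and so depends on the mix. The case for change rests on its low cost, not on a demonstrated bias.

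**What to change.** - **Section 8.2:** randomise owners of an NFC phone within two strata (NA, leg prosthesis), using small random blocks.
- **Section 10.1:** for the between-group comparison, replace the paired test by a linear model of end ESES on arm, baseline ESES and diagnosis. The section has no regression model for this comparison at present, so the test itself has to change; a covariate cannot simply be added to it.
- **Reporting:** show ESES change, SUS and app use by diagnosis descriptively, without subgroup p-values.
- **State the limits:** stratification cannot remove imbalance from patients without an NFC phone, who enter only the control arm, so adjustment for diagnosis is needed as well. Selection on other factors related to phone access remains. The prosthesis stratum merges socket and osseointegrated users, a compromise at this sample size.

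The cost is two short allocation lists and one degree of freedom: a standard error of about 0.37 instead of 0.36 SD if diagnosis has no effect. The sample size does not change, and no new data are needed.

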6.2 Summary of findings from non-clinical studies

In the past year, Radboudumc organised two sprint days. During these days, patients, physiotherapist, researchers and Touchless Industries discussed the fit of new innovations into the healthcare sector. The aim of the sprint was to determine the need for integration of exercises into daily activities. The needs of all parties were scanned and all ideas were combined into a first prototype. The prototype consisted of NFC stickers, which could be scanned by a NFC-compatible Android phone or tablet presenting interesting content on the mobile device. The prototype was tested the same day, where stickers were placed in a living room like environment.

The first sprint included a patient affected by hereditary spastic paraplegia (HSP) during rehabilitation. In this prototype, the stickers were linked to videos of physiotherapy exercises, which could help them perform their exercises in a better way. The HSP patient on site saw great potential in this application, because it would guide him through his daily exercises. This sprint is the foundation and idea for the project “sticking to your exercises”. Based on the potential seen by all included parties, there is a need for further development and evaluation of this idea, investigated in this pilot study.

The second sprint was focussed on an osseointegrated prosthesis wearer. This session was used to determine the potential of this new technology and to get a first design of the implementation into the regular treatment. Again, patient, physician and developers were enthusiastic about the idea and wanted to further investigate the possibilities of this technology used in clinical practice. After this session, the project team and developers were able to assemble the first design, presented in this pilot study.

6.3 Summary of findings from clinical studies

Not applicable, no clinical studies have been carried out yet.

6.4 Summary of known and potential risks and benefits

Risks

Wrong positioning of the tags.

Exercises are executed on mismatched locations, which may lead to non-optimal performance or worse injuries due to obstacles. This risk will be reduced by designing the NFC-tags with a clear label indicating the appropriate location. In addition, the physiotherapist will be instructed on how to hand out the tags to the participating patients.

Benefits

More insight into the real data of home therapy/Improved communication between patient and physiotherapist.

Because patients monitor their exercises, the application data can be used during physiotherapist meetings to discuss the activities of the patient during his/her home sessions. Using the application the physiotherapist is provided with the real activity data instead of the being dependent on the memory ability of the patients. As data regarding therapy is more accurate, this allows for adequate adaptation of therapy if necessary.

Rehabilitation might be improved by increased therapy adherence and a different instruction method for exercises in home environment.

Due to the video instructions, patients will get visual feedback on their home exercises by comparing their own performance to the example on their phone. Besides improvement on correct performance of the exercise, we also expect an increase on therapy adherence. There are more and smarter (location based) reminders making it likely that the frequency of exercises increases.

6.5 Description and justification of route of administration and dosage

Not applicable

6.6 Dosages, dosage modifications and method of administration

Not applicable

6.7 Preparation and labelling of Investigational Medicinal Product

Not applicable

6.8 Drug accountability

Not applicable

7. NON-INVESTIGATIONAL PRODUCT

Not applicable

- 7.1 Name and description of non-investigational product(s)**
- 7.2 Summary of findings from non-clinical studies**
- 7.3 Summary of findings from clinical studies**
- 7.4 Summary of known and potential risks and benefits**
- 7.5 Description and justification of route of administration and dosage**
- 7.6 Dosages, dosage modifications and method of administration**
- 7.7 Preparation and labelling of Non Investigational Medicinal Product**
- 7.8 Drug accountability**

8. METHODS

8.1 Study parameters/endpoints

8.1.1 Main study parameter/endpoint

We will assess the self-efficacy during exercising. Self-efficacy reflects an individual's belief in his or her ability to engage in specific behaviours that will yield a desired outcome. Self-efficacy beliefs are important because the belief that one can exercise, even given constraints and impediments such as feeling tired or being busy, is associated with a greater likelihood of doing it (Neupert *et al.*, 2009).

